The primary objectives of this study are to compare the therapeutic impact of liraglutide 368 3 mg versus placebo on reduction of body weight and biochemical hyperandrogenism (as 369 determined by the free androgen index) in obese non-diabetic women with PCOS. We will 1) 370 determine the percentage of participants achieving \geq 5% reduction in baseline body weight with 371 each treatment and 2) assess the inhibition of biochemical hyperandrogenism (ovarian androgen 372 production and sex hormone binding capacity) in response to each treatment.

373 Secondary study objectives

The secondary study objectives are to determine the effect of treatment with antiobesity medication versus placebo on anthropometric, **clinical**, hormonal and metabolic parameters in non-diabetic obese women with hyperandrogenism.

377

378 EFFICACY VARIABLES/MEASURES

379 *Primary endpoints*

The co-primary end points are to compare obese women with PCOS receiving liraglutide 3mg (LIRA 3 mg) with those receiving placebo on body weight and bioavailable ovarian androgen

- 382 concentrations as determined by:
- 1a. percent change in body weight from baseline to week 30 and
- 1b percentage of participants achieving ≥5% reduction in body weight from baseline
 to week 30
- 3862reduction of free androgen index [FAI=testosterone (T)/sex hormone binding387globulin (SHBG) levels] from baseline to 30 weeks
- 388 Secondary endpoints
- 389 We will further examine the impact of the administration of these pharmacotherapies in obese
- 390 non-diabetic PCOS women on:
- 391 Anthropometric and Clinical Indices
- Change from baseline of body mass index [BMI], absolute body weight, waist circumference (WC), waist: hip ratio (WHR), waist-height ratio (WHtR), and whole-body dual-energy X-ray absorptiometry [DXA]) measures of body composition (trunk fat mass and truck fat/extremities fat ratio) to determine the relative contribution of changes in fat mass (FM) vs. lean mass (LM) to overall weight loss at week 30
- 2. Compare women with hyperandrogenism for frequency of patients achieving a body
 weight reduction of at least 10% [Time Frame from baseline to 30 weeks]
- 399 3. Change in menstruation frequency (normalized to the number of menstruations per year) from before and after 30 weeks of treatment
- 401 Metabolic Parameters
- 402 1. Change in glycemic values from baseline to 30weeks
- 403 2. Fasting and 2 hour glucose levels after an OGTT

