During the study period, cycle control will be assessed daily by the subjects using a menstrual diary. Vaginal bleeding will be classified by the subject as either spotting (requiring at least one pad/tampon per day) or bleeding (two or more pads/ tampons per day). The effects of treatment intervention on menstrual abnormalities will be evaluated by assessing posttreatment changes in menstruation frequency over 30 weeks from the patient's menstrual cycle diary and normalized to the number of menstruations per year (52 weeks).

All side-effects will also be recorded and summarized for the 30 week-treatment period. During the whole study period, compliance to the treatment will be documented. Compliance with treatment will be checked by questioning about the side-effects and a subjective evaluation of the tolerability of the administered drug; the patients will also asked about incidental missed administrations and whether they had correctly followed the scheduled treatment. Questioning regarding the occurrence of adverse events and use of concomitant medication will take place throughout the trial.

655

656 Study Medication

657 Study Drug Storage- All investigational products (study drugs) will be stored under 658 appropriate storage conditions in a secure area according to local regulations. The investigator is responsible for ensuring that it is dispensed only to study subjects and only from official study 659 660 sites by authorized personnel, as dictated by local regulations. The investigator is responsible for 661 ensuring that the investigational product is stored under the appropriate environmental 662 conditions (temperature, light, and humidity), as noted in the product labeling. Novo Nordisk 663 will supply all investigational products. The distribution of all supplied medications is the 664 investigators' responsibility.

665 *Study Drug Records*- It is the responsibility of the investigator to ensure that the 666 unblinded study coordinator maintains a current disposition record of investigational product. 667 Records or logs must comply with applicable regulations and guidelines and should include:

- 668
- 669

672 673

674

675

- amount received and placed in storage area; amount currently in storage area
- label ID number or batch number
- amount dispensed to and returned by each subject, including unique subject
 identifiers
 - non-study disposition (e.g., lost, wasted)
 - amount destroyed at study site

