For all analyses, in which the measures are continuous, data from evaluable subjects will be submitted to a repeated-measures general linear model (SS/ Drug treatments x repeated measures ANOVA) including the arm of drug treatment (liraglutide 3mg vs. placebo) as the between-subjects effect, and the visit (baseline and 30 wks) as the within-subjects effect. To evaluate the differences in the response to each treatment over visits, the interaction effect will be calculated. Baseline comparisons between groups will be made by one-way ANOVAs.

Frequency of patients achieving a body weight reduction of at least 5% and 10% before and after treatment will be compared with the McNemar test (complex chi square $[\chi^2]$ for paired data), which formally tests for a change between the observed proportions of k related samples. Dysglycemia occurrence before and after different treatment will also be compared with the McNemar test. The difference in frequency of menstruation before and aftertreatment will also be compared using the McNemar test.

Data will be analyzed on completed treatment parameters where relevant (evaluable population). The evaluable population is defined as all randomized subjects who complete treatment through week 30-32 week. Results will be reported as mean +/- S.E.M for normally distributed data and as median (interquartile range) if the distribution is not normal. Categorical data will be presented as percentage. P < 0.05 is considered statistically significant.

773

774 Sample Size and Justification

775 A priori sample size analysis was performed using the online calculator provided by the 776 Hospital Mallinckrodt General Clinical Massachusetts General Research Center (http://hedwig.mgh.harvard.edu/sample size/size.html). To calculate sample size, we used the 777 778 standard formula suggested for clinical trials by considering a type one error (α) of 0.05 and type 779 two error (β) of 0.20 (power = 80%). Sample size calculation revealed that 57 participants 780 randomized in a 2:1 ratio (liraglutide: placebo) were needed. Using a 30% drop-out rate, the 781 study is designed to recruit 92 patients, enroll 48 liraglutide and 24 placebo to ensure that the 782 number of subjects completing the study (38 LIRA/19 PL) as derived by the sample size 783 calculation is met.

784

785 Ethical and Regulatory Requirements

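### The ≥5% weight-loss co-primary endpoint is given a before/after McNemar test, which cannot compare liraglutide with placebo and is degenerate for a response measured from baseline

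*Combined protocol and SAP*

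**What the plan says.** The Primary endpoints section sets out the aim: "The co-primary end points are to compare obese women with PCOS receiving liraglutide 3mg (LIRA 3 mg) with those receiving placebo". Item 1b in that list is the "percentage of participants achieving ≥5% reduction in body weight from baseline" to week 30. Under Secondary endpoints, ≥10% loss is a further responder outcome, and the menstrual outcome is "Change in menstruation frequency (normalized to the number of menstruations per year) from before and after 30 weeks of treatment".

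Statistical Methods then assigns the tests. For both weight-loss thresholds, the frequency of patients with a "body weight reduction of at least 5% and 10% before and after treatment will be compared with the McNemar test". The plan describes this as a test for paired data, "which formally tests for a change between the observed proportions of k related samples". Dysglycemia receives the same before/after test. So does menstruation: "The difference in frequency of menstruation before and aftertreatment will also be compared using the McNemar test".

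The only analysis that compares outcomes between arms is the repeated-measures general linear model with its arm-by-visit interaction, and the plan restricts it to continuous measures. No between-arm test is named for any binary outcome.

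**The concern.** Women on liraglutide and women on placebo are independent groups. McNemar's test takes two binary readings on the same woman and asks whether the proportion changed, so it cannot answer the randomised question in 1b.

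For weight-loss response the difficulty goes further. Response is defined relative to baseline, so the baseline reading is always non-response. All the test can then ask is whether some women lost 5%.

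At stake is a listed co-primary endpoint with no valid test of drug effect. Run separately in each arm, the test invites the reading that a significant result on liraglutide beside a non-significant one on placebo shows efficacy. With 2:1 allocation, that pattern can arise easily with no drug effect.

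**Working it through.** **Inputs.** From Sample Size and Justification: 38 liraglutide and 19 placebo completers, 57 in total. From Statistical Methods: significance at P < 0.05. Sidedness is not stated, and two-sided is used here. The documents give no responder rates, so all rates below are assumptions. The plan's figure of 57 cannot be reproduced, because no effect size, SD or response rate is given; nothing below depends on how it was derived.

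**Step 1: the test statistic.** Let b be the women who are non-responders before and responders after, and c the reverse. Since nobody is a responder at baseline, c = 0 and b = r, the number of responders.

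- Exact two-sided p = 2 × 0.5^r. For r = 5: 2 × 0.03125 = 0.0625. For r = 6: 2 × 0.015625 = 0.031.
- Uncorrected chi-square = (b − c)²/(b + c) = r. For r = 4, p = 0.046.
- Continuity-corrected chi-square = (r − 1)²/r. For r = 6: 25/6 = 4.17, p = 0.041.

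The plan does not say which version applies. On the exact or corrected version, six responders are enough: 6/38 = 15.8% on liraglutide and 6/19 = 31.6% on placebo. The other arm has no influence.

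**Step 2: an example with identical response.** Take 12/38 and 6/19, both 31.6%. McNemar gives p = 0.0005 on liraglutide, 0.031 on placebo and 7.6 × 10⁻⁶ pooled. Fisher's exact test between arms gives p = 1.00.

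**Step 3: behaviour with no drug effect.** Suppose both arms share a true response rate. Let A = P(r ≥ 6) from Binomial(38, rate) and B = P(r ≥ 6) from Binomial(19, rate). The chance of significance on liraglutide only is A × (1 − B).

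| Common rate (assumed) | A: liraglutide significant | B: placebo significant | Liraglutide only | Pooled 57 significant | Fisher between arms |
|---|---|---|---|---|---|
| 5% | 0.011 | <0.001 | 0.011 | 0.065 | 0.014 |
| 10% | 0.175 | 0.009 | 0.173 | 0.511 | 0.027 |
| 15% | 0.515 | 0.054 | 0.487 | 0.875 | 0.034 |
| 20% | 0.800 | 0.163 | 0.669 | 0.981 | 0.036 |
| 25% | 0.940 | 0.332 | 0.627 | 0.998 | 0.036 |
| 30% | 0.986 | 0.526 | 0.467 | >0.999 | 0.036 |
| 40% | >0.999 | 0.837 | 0.163 | >0.999 | 0.037 |
| 50% | >0.999 | 0.968 | 0.032 | >0.999 | 0.034 |

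For the 20% row: 0.800 × (1 − 0.163) = 0.669.

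**Step 4: the proper test at the planned size.** With 38 and 19 completers, Fisher's test at two-sided 0.05 has power 0.81 for 60% versus 20% response, 0.67 for 60% versus 25%, and 0.56 for 50% versus 20% (assumed rates). For 24/38 versus 5/19 it gives p = 0.012.

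**Step 5: the other outcomes.** Dysglycemia can be present at baseline, so c need not be zero and McNemar is a legitimate test of change within an arm. It still does not compare arms. Menstrual frequency is a count scaled to 52 weeks. McNemar needs a binary variable, and no cut-off is given for this analysis.

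**The case against.** **Status of 1b.** The list of primary endpoints in Statistical Methods names only percent weight change and free androgen index, and both have an arm-by-visit test. The trial therefore keeps a randomised comparison of weight, on the same data that 1b dichotomises. This limits the damage and shows an inconsistency that needs reconciling. It does not give 1b or ≥10% loss a usable test, and the test would be wrong for a secondary endpoint too.

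**The size range.** Rates of 15% to 30% lie around the peak of the curve. At 5% or 10% the chance of the misleading pattern is 1% or 17%; at 40% or 50% it is 16% or 3%. The plan does not make that pattern its decision rule, and it does not clearly propose pooling the arms. Both points are fair. The probabilities describe a likely misreading, not a stated type I error rate. The structural fault holds at every rate.

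**Menstrual frequency and dysglycemia.** A yearly rate could be read as falling under the continuous-measures model, and the eligibility criterion of fewer than eight cycles a year could supply a binary form. However, the explicit assignment is McNemar, and that cut-off is not invoked for it. Dysglycemia is the milder case: it is not listed by name among the endpoints, and fasting and 2-hour glucose are compared between arms as continuous measures.

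**Conclusion.** The concern holds. As written, ≥5% response (co-primary 1b), ≥10% response and dysglycemia have no between-arm test, and menstrual frequency is assigned a test that does not fit its data type. For the two weight-loss responses the assigned test is degenerate: its p-value depends only on the number of responders, and six are enough on the exact test.

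If the drug had no effect, the chance of significance on liraglutide alone is 0.47 to 0.67 at common response rates of 15% to 30%, and 0.01 to 0.17 at the lower and higher rates examined. These figures assume 38 and 19 completers, two-sided 0.05, the exact test and equal true response in both arms. The fault itself needs none of these assumptions. Percent weight change and free androgen index are not affected.

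**What to change.** Replace McNemar in Statistical Methods with prespecified between-arm analyses:

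- **≥5% and ≥10% loss at week 30:** compare arms by Fisher's exact test, or by logistic regression on arm and baseline weight. Name one of these in advance as the primary method, and report the risk difference with a 95% confidence interval.
- **Dysglycemia at week 30:** logistic regression on arm and baseline dysglycemia.
- **Menstrual frequency:** a between-arm model adjusted for menses in the prior 12 months. This could be a negative-binomial model of diary menses with log weeks of diary as offset, or ANCOVA on menses per year.

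Only the between-arm comparison is essential; the covariates and the count model are recommendations. Within-arm changes may stay as description. The list of primary endpoints in Statistical Methods should also be reconciled with the Primary endpoints section on the status of 1b.

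The cost is revised text. Weights, OGTT results, prior-year menses and diaries are already collected, so no visits or patients are added. Under Ethical and Regulatory Requirements the revision is a protocol amendment needing advance written approval from the review board.

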The United States Food and Drug Administration (FDA) have assigned pregnancy category X to Saxenda (3 mg liraglutide). Studies in animals or humans have demonstrated there is positive evidence of human fetal risk based on adverse reaction data from investigational or marketing experience, and the risks involved in use of the drug in pregnant women clearly outweigh potential benefits. Safer alternatives exist. If patients become pregnant during the study, all medications will be stopped and the patient will discontinue from the study.

For safety, all subjects who enter the study are evaluable. Subjects will be monitored for safety by assessment of adverse events, physical exams, vital signs and laboratory values. Continued patient safety assessment will be carried out and all adverse events documented and reported to the WHIRB. On each visit, compliance with treatment will be checked with questions about the side-effects and a subjective evaluation of the tolerability of the administered drug; the patients will also asked about incidental missed administrations.

Adverse events will be evaluated on a continuous basis while the patient is on study and until 30 days after the last dose of study drug. Patients should be followed until all treatmentrelated adverse events have recovered to baseline or are deemed irreversible by the principal investigator.

826

827 Adverse Event Procedures

An Adverse Event (AE) is defined as any new untoward medical occurrence or worsening of a preexisting medical condition in a clinical investigation subject administered an investigational (medicinal) product and that does not necessarily have a causal relationship with this treatment. An AE can therefore be any unfavorable and unintended sign (such as an abnormal laboratory finding), symptom, or disease temporally associated with the use of investigational product, whether or not considered related to the investigational product.

An Adverse Reaction (AR) is defined as any untoward and unintended responses to an investigational medicinal product related to any dose administered Thus, for an AR, a causal relationship must be at least suspected by the medical practitioner. Unexpected Adverse Reaction (UAR) is an adverse reaction, the nature or severity of which is not consistent with the applicable product information (e.g. investigator's brochure for an investigational product or summary of product characteristics for an authorized product).

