1021 Any significant worsening noted during interim or final physical examinations, 1022 electrocardiogram, x-ray filming, any other potential safety assessment required or not required 1023 by protocol should also be recorded as a nonserious or serious AE, as appropriate.

- 1024
- 1025 Discontinuations

1026 The reason for a subject discontinuing from the study will be recorded in the patient chart. 1027 A discontinuation occurs when an enrolled subject ceases participation in the study, regardless 1028 of the circumstances, prior to completion of the protocol. The investigator must determine the 1029 primary reason for discontinuation. Withdrawal due to adverse event will be distinguished from 1030 withdrawal due to insufficient response according to the definition of adverse event noted 1031 earlier. The final evaluation required by the protocol will be performed at the time of study discontinuation. The investigator will record the reason for study discontinuation, provide or 1032 1033 arrange for appropriate follow-up (if required) for such subjects, and document the course of the subject's condition. They will also to be reported to Woman's Hospital Foundation 1034 1035 Institutional Review Board at [contact] and Woman's Health Research Department at 1036 [contact].

1037

1038

Subjects MUST discontinue investigational product for any of the following reasons:

- Withdrawal of informed consent (subject's decision to withdraw for any reason).
- Any clinical adverse event, laboratory abnormality, or intercurrent illness, which, in
 the opinion of the investigator, indicates that continued participation in the study is
 not in the best interest of the subject.
- 1042 Pregnancy
- 1043oInstruct subjects to contact the investigator or study staff immediately if they1044suspect they might be pregnant (e.g., missed or late menstrual period) at any1045time during study participation. Institutional policy and local regulations should1046determine the frequency of study pregnancy tests for subjects enrolled in the1047study.
- 1048oThe investigator must immediately notify Novo Nordisk if a study subject1049becomes pregnant.
- Loss of ability to freely provide consent through imprisonment or involuntary incarceration for treatment of either a psychiatric or physical (e.g., infectious disease) illness.

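### The continuous co-primary endpoints, percent weight change and FAI, are analysed only in women who complete treatment, which leaves out 15 to 22 of the 72 randomised and can bias the comparison either way

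*Combined protocol and SAP*

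**What the plan says.** All references are to the combined protocol and SAP.

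- **Continuous measures (Statistical Methods).** For all such analyses, "data from evaluable subjects will be submitted to a repeated-measures general linear model", with treatment arm as the between-subject factor and visit (baseline and week 30) as the within-subject factor. The same section names percent weight change and FAI as the primary endpoints, so both fall under this rule.
- **General rule (Statistical Methods).** "Data will be analyzed on completed treatment parameters where relevant (evaluable population"). The population is then defined: "The evaluable population is defined as all randomized subjects who complete treatment through week 30-32 week".
- **Responders.** The primary endpoints under Efficacy Variables/Measures also include the share of women losing at least 5% of body weight. No denominator is named for it, so completers are the natural reading.
- **Sample Size and Justification.** "Using a 30% drop-out rate", 48 women are to be enrolled on liraglutide and 24 on placebo, to secure the "number of subjects completing the study (38 LIRA/19 PL").
- **Safety (Ethical and Regulatory Requirements).** "For safety, all subjects who enter the study are evaluable". No matching statement exists for efficacy.
- **Discontinuations.** Withdrawal for an adverse event is to be distinguished from "withdrawal due to insufficient response according to the definition of adverse event noted" earlier. Also: "The final evaluation required by the protocol will be performed at the time of study discontinuation". Women who withdraw consent for all procedures, or who can no longer consent freely, are exempt from follow-up.
- **Study Assessments, part C.** Weight is measured at week 16-18. Testosterone and SHBG are not.

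**The concern.** Randomisation makes the 48 and 24 women comparable. It does not do so for those who remain after some have left for reasons linked to treatment or response. The plan foresees two such reasons, adverse events and insufficient response, and they may act differently in the two arms. The protocol lists nausea, vomiting and diarrhoea as common with the drug, while lack of effect could plausibly drive more women off placebo.

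Selective loss can therefore make the liraglutide effect look larger or smaller than it is, and the completers alone cannot show which. Responder rates within each arm are likely to be too high; they are not only if women who leave reach 5% loss as often as those who stay. Data that would help, namely the week 16-18 weight and the evaluation at discontinuation, are collected but given no efficacy role.

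**Working it through.** **1. How many women are left out**

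Inputs: 72 randomised (48/24), 57 planned completers (38/19) and 30% drop-out, all from Sample Size and Justification.

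- From the completer count: 72 - 57 = 15 (10 liraglutide, 5 placebo), and 15/72 = 20.8%.
- From the stated rate: 0.30 × 72 = 21.6, about 22.

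The two figures disagree. Allowing for 30% drop-out, 57/0.70 = 81.4, or 82 women, so the plan's 72 is not reproduced. At 20%, 57/0.80 = 71.25, or 72. That mismatch is a separate point; here it only sets the range of 15 to 22.

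**2. The bias formula**

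Let d be the drop-out proportion and g the completer mean minus the drop-out mean, within an arm. The completer difference (liraglutide minus placebo) departs from the all-randomised difference by

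d(L) × g(L) - d(P) × g(P).

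This is zero only if the product is the same in both arms. If completers are assumed to lose 5 points more than drop-outs in one arm only, with equal drop-out, the shift is 0.208 × 5 = 1.04 points or 0.30 × 5 = 1.50 points. It favours liraglutide if that arm is liraglutide, and goes against it if that arm is placebo.

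**3. Weight-change scenarios**

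These inputs are assumptions, since the plan gives none: true effect -4.0 points, SD 6, and logit(drop-out) = a + slope × z. Here z is the week-30 response in SD units (positive means poorer), and a is set to give the stated drop-out rate. Completer means come from numerical integration. Type I error (no drug effect, two-sided 5% t-test) comes from simulated trials of 48/24.

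| Slope L/P | Drop-out L/P | Completer estimate | Type I error |
|---|---|---|---|
| 1 / 0 | 35% / 20% | -5.8 | 18% |
| 1 / 0 | 30% / 30% | -5.5 | 15% |
| 1 / 0 | 20.8% / 20.8% | -5.1 | 10% |
| 0.5 / 0 | 35% / 20% | -5.0 | 9% |
| 1 / 1 | 35% / 20% | -4.7 | 7% |
| 0.5 / 0.5 | 35% / 20% | -4.4 | 6% |
| 0.5 / 0.25 | 30% / 30% | -4.4 | 6% |
| 0.5 / 0.25 | 20.8% / 20.8% | -4.3 | 5% |
| 1 / 1 | 30% / 30% | -4.0 | 5% |
| 1 / 1 | 20% / 40% | -3.1 | 8% |
| 0 / 1 | 20.8% / 20.8% | -2.9 | 9% |
| 0 / 1 | 30% / 30% | -2.5 | 13% |
| 0 / 1 | 25% / 40% | -2.0 | 18% |

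In the first row nearly all false positives favour liraglutide; in the last nearly all favour placebo.

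**4. Responders**

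Assume completer rates of 60% and 20%, a 40-point difference. The all-randomised difference is then bounded by the two extreme outcomes for the missing women.

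- 15 missing (38/19 complete): lower (22.8/48) - (3.8 + 5)/24 = 10.8 points; upper (22.8 + 10)/48 - 3.8/24 = 52.5 points.
- 22 missing (34/16 complete): lower 20.4/48 - (3.2 + 8)/24 = -4.2 points; upper (20.4 + 14)/48 - 3.2/24 = 58.3 points.

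Counting drop-outs as non-responders gives 40 × 0.70 = 28 points at 30% drop-out and 40 × 0.792 = 31.7 at 20.8%. With unequal drop-out it gives 0.6 × 0.6 - 0.2 × 0.9 = 18 points (40%/10%) or 0.6 × 0.9 - 0.2 × 0.6 = 42 points (10%/40%).

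**5. Does an all-randomised model help?**

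Assume a correlation of 0.8 between week 16-18 and week-30 change. The cases are the first and last rows of the table, and the true effect is -4.0.

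| Drop-out depends on | Completers | Model, week 16-18 weight known for all | Model, half of drop-outs lack it |
|---|---|---|---|
| Week 16-18 value | -5.4 / -2.4 | -4.0 / -4.0 | -4.6 / -3.4 |
| Unseen week-30 value | -5.8 / -2.0 | -4.7 / -3.2 | -5.1 / -2.8 |

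The model moves the estimate towards the truth in every case, but not always all the way.

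**The case against.** The strongest reply has four parts.

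- **The largest biases come from corner cases.** They need strong response-related drop-out in one arm, none in the other and, at the extremes, unequal rates. The documents support none of these inputs. This stands as a caution: milder patterns shift the estimate by only 0.3 to 0.4 points and leave type I error at 5% to 6%, so anything from negligible to large bias fits the plan. The point does not need the extremes, because the completer data cannot tell these cases apart.
- **The non-responder figures are not a measure of bias.** Correct. They show what a different endpoint definition would give, and they move with drop-out imbalance alone. The bounds in step 4 show what the missing women leave uncertain.
- **The remedy is imperfect.** Women who leave before week 16 have no interim weight, exit evaluations are not at week 30, and FAI has no interim value. This also stands, and is why a sensitivity analysis is part of the change.
- **A completer analysis can suit a small efficacy study.** It can as support. Here it is the only efficacy analysis of the continuous endpoints in a trial whose hypothesis is a randomised comparison.

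The qualifier in the general rule does not rescue the continuous endpoints, because the model sentence covers all of their analyses.

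**Conclusion.** The concern holds and must be fixed. Percent weight change and FAI are both restricted to completers, and nothing elsewhere in the plan supplies an all-randomised efficacy analysis. The exclusion of 15 to 22 of 72 women (20.8% to 30%) follows from the plan's own figures. The possible bias in weight change, from no shift to about 2 points in either direction on an assumed true effect of -4.0, rests on the assumed SD, slopes and drop-out rates in the table. Neither its direction nor its actual size can be predicted. FAI is exposed to the same mechanism, but the plan gives no figures from which to illustrate it.

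**What to change.** - **Population.** Make the primary efficacy analysis all randomised women, in the arm to which they were randomised, and state the estimand. Keep completers as supportive.
- **Percent weight change.** Use a mixed model or multiple imputation with baseline, week 16-18 and final weights, entering early-termination weights at their actual time.
- **FAI.** Multiply impute the week-30 value, using baseline and any discontinuation value as predictors. The discontinuation value enters at its actual time and is not carried forward.
- **Responders (at least 5% and 10%).** Count a woman without a week-30 weight as a non-responder, stated as part of the endpoint definition, and report drop-out by arm beside it.
- **Sensitivity.** Add an analysis for data not missing at random.
- **Wording.** Reconcile the completer definition, which runs to week 30-32, with the 28-30 week treatment period stated elsewhere.

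The cost is SAP wording and modest programming. A model- or imputation-based analysis needs no new visits. If the chosen estimand counts outcomes regardless of stopping treatment, week-30 measurements after discontinuation would be wanted. The protocol does not date its follow-up after discontinuation, so that choice could add visits. The estimated effect may be smaller than in completers, and the main analysis rests on a missing-at-random assumption that the sensitivity analysis has to test.

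### The plan does not commit to reporting the liraglutide-minus-placebo difference with a confidence interval for any endpoint, including the co-primaries

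*Combined protocol and SAP*

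**What the plan says.** The rule is in the STATISTICAL/ANALYTICAL PLAN, under Statistical Methods. For continuous data: "Results will be reported as mean +/- S.E.M for normally distributed data and as median (interquartile range) if the distribution is not normal". For categorical data: "Categorical data will be presented as percentage". The decision criterion is "P < 0.05 is considered statistically significant".

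Continuous measures go into a repeated-measures model with treatment arm as the between-subjects effect "and the visit (baseline and 30 wks) as the within-subjects effect". The comparison of arms is described in one sentence: "To evaluate the differences in the response to each treatment over visits, the interaction effect will be calculated". For responders, "Frequency of patients achieving a body weight reduction of at least 5% and 10% before and after treatment will be compared with the McNemar test".

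The same section allows log or square-root transformation of non-normal variables before testing. It does not say whether the mean and SEM refer to values at each visit or to changes. Neither there nor under Primary endpoints or Sample Size and Justification is a confidence interval, a reported treatment difference or a standard error of one mentioned.

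The co-primary endpoints under EFFICACY VARIABLES/MEASURES are "percent change in body weight from baseline to week 30", the proportion losing at least 5% of body weight, and the reduction in free androgen index (FAI).

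**The concern.** The primary objective is comparative, so the main result should be an estimate of how much more liraglutide does than placebo, and how precisely that is known. The reporting rule asks for one summary per arm and a significance verdict. A report that followed it to the letter could omit the treatment effect and its interval for every endpoint.

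Three consequences follow.

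- **Non-significant results.** With 57 completers, a P-value above 0.05 for FAI could mean little effect or a wide interval. Only the interval tells these apart. The sample-size section gives no target effect or SD, so the reader has no other yardstick.
- **Transformed endpoints.** A variable tested on the log scale but summarised as median (IQR) would have its P-value on one scale, a measure of spread on another, and no effect estimate on either.
- **Responders.** A before-and-after test does not compare the arms. Two percentages would be printed with no between-arm inference attached.

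**Working it through.** **Inputs from the documents.** Two arms and two visits (Statistical Methods). Planned completers are 38 liraglutide and 19 placebo, total 57 (Sample Size and Justification). The plan gives no interval width, effect size or SD, so it has no figure of its own on this point to reproduce. The completer target is taken at face value.

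**Assumptions not in the documents.** A common SD in both arms and at both visits, and a within-woman baseline-to-week-30 correlation r, shown over a range.

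**Step 1: what the interaction is.** With two arms and two visits it has one degree of freedom and equals D = (mean change on liraglutide) − (mean change on placebo). Its test is the two-sample t test on change, with 38 + 19 − 2 = 55 degrees of freedom. The contrast needed is therefore already in the planned model.

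**Step 2: if the SEMs are of change.** In units of the SD of change:

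- liraglutide SEM = 1/√38 = 0.162; placebo SEM = 1/√19 = 0.229
- SE(D) = √(0.162² + 0.229²) = √(1/38 + 1/19) = 0.281
- 95% CI half-width = 2.004 × 0.281 = 0.563

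The interval can be rebuilt from the two printed SEMs. For percent weight change with an assumed SD of 4 to 7 percentage points, the half-width is 0.563 × 4 = 2.3 to 0.563 × 7 = 3.9 points.

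**Step 3: if the SEMs are of visit values.** Combining the two week-30 SEMs again gives 0.281, now in units of the SD at a visit. The tested contrast has SE(D) = 0.281 × √(2(1 − r)). The last column takes equal baseline means and week-30 SEM bars that just touch, so D = 0.162 + 0.229 = 0.392 (from unrounded terms).

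| r (assumed) | SE(D), visit SDs | 0.281 / SE(D) | Interaction P when bars just touch |
|---|---|---|---|
| 0.3 | 0.332 | 0.85 | 0.24 |
| 0.5 | 0.281 | 1.0 | 0.17 |
| 0.90 | 0.126 | 2.2 | 0.003 |
| 0.95 | 0.089 | 3.2 | 0.00005 |
| 0.97 | 0.069 | 4.1 | 0.0000005 |

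The same printed summaries can go with a null or a very strong interaction. Without r, the precision of the contrast cannot be recovered.

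**Step 4: why the interval matters for a null result.** Working back from 38 and 19 completers, 80% power and two-sided 0.05, the t test detects a standardised difference of about 0.80. The plan states neither this figure nor the sidedness. Suppose the observed difference in change is 0.30 SD. Then t = 0.30/0.281 = 1.07, P = 0.29, and the 95% CI is 0.30 ± 0.563, or −0.26 to 0.86. That includes both zero and 0.80. The P-value alone would not show this.

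**Step 5: responders.** Before treatment no woman has yet lost 5% from baseline, so the paired comparison sets a proportion that is zero by definition against a later one. It contains no contrast between arms. The missing quantity is the risk difference. Its SE is at most 0.5 × √(1/38 + 1/19) = 0.140, since p(1 − p) cannot exceed 0.25. The approximate 95% half-width is thus at most 1.96 × 0.140 = 0.275, or about 28 percentage points.

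**The case against.** The strongest reply is that this is a matter of presentation. The interaction is to be calculated, and it is the difference in mean change. On an untransformed scale a reader can get its size by subtracting arm means. If an exact P is printed, the SE follows as the difference divided by t. The weight and FAI co-primaries are defined as changes, so SEMs of change would be natural, and Step 2 shows that these suffice. No test, sample size or data collection is affected.

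Much of this stands, and it rules out several stronger readings that a reader might infer.

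- **That the treatment difference is never estimated.** The interaction sentence says otherwise. What is missing is a requirement to report it with an interval.
- **That means with SEM are all that will be shown.** The rule also provides for medians with IQR and for percentages. These give no treatment difference either.
- **That the printed SEMs overstate the uncertainty 2.2 to 4.1 times.** This holds only for SEMs of visit values with r between 0.90 and 0.97. The factor is 1.0 at r = 0.5 or when SEMs of change are combined, and below 1 at r = 0.3. The documents give no correlation and do not say which SEM is meant.
- **That 2:1 allocation makes the SEMs misleading.** At equal SD the placebo SEM is √(38/19) = 1.41 times the liraglutide SEM. This is correct, because a mean of 19 is less precise than a mean of 38.

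The reply does not close the gap. The plan promises neither SEMs of change nor exact P-values. Subtraction does not help when medians are shown for a variable tested after transformation. For responders, no planned analysis gives a between-arm estimate.

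**Conclusion.** The point holds as an omission from the reporting rule: no endpoint, co-primary or secondary, has a required between-arm estimate with a confidence interval. The consequence depends on the endpoint.

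- For untransformed continuous endpoints, the contrast is computed but need not be shown. Its precision is recoverable from SEMs of change and not from SEMs of visit values.
- For transformed endpoints, the prescribed summary does not match the scale tested.
- For the responder endpoints, including the 5% co-primary, no between-arm estimate is planned.

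The information at stake is an interval of about ±0.56 SD of change for continuous endpoints, and at most about ±28 percentage points for responders. Both figures assume 38 and 19 completers; the first also assumes equal SDs. Everything involving r is illustrative. The continuous tests are not made invalid. The change should still be made before analysis, because it determines whether a positive result can be sized and a null result interpreted.

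**What to change.** Replace the reporting rule in Statistical Methods with the following.

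- **Description.** Each arm at each visit: mean (SD), or median (IQR) if skewed, with the number of women. Label whether a summary is of visit values or of change.
- **Continuous endpoints.** The liraglutide-minus-placebo difference in mean change (mean percent change for body weight) with its 95% CI.
- **Log-transformed endpoints, such as FAI if it is transformed.** The between-arm ratio of geometric means (week 30 relative to baseline) with its 95% CI. If the square-root option is kept, its effect measure must be named in advance, since a ratio of geometric means does not apply to it.
- **Responders at 5% and 10%.** Each arm's proportion and the between-arm risk difference with its 95% CI.
- **Interpretation.** Base conclusions on the estimates and intervals, and give exact P-values as secondary information.

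**Cost.** The continuous estimates come from the models already planned. The responder comparison is not among those models and needs one simple additional two-arm analysis of data already collected. Sample size, visits and measurements do not change.
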